14. QUALITY CONTROL AND QUALITY ASSURANCE

To ensure compliance with GCP and all applicable regulatory requirements, the Sponsor / designee may conduct a quality assurance audit. Please see Section 13.2 for more details regarding the audit process.

15. ETHICS

15.1. Institutional Review Board/Independent Ethics Committee Approval

Before initiation of the study, the Investigator must obtain approval or favorable opinion of the research protocol, ICD, and any material related to patient recruitment from an IRB or IEC. For locations participating within the US, the IRB must comply with the provisions specified in 21 Code of Federal Regulations (CFR) Part 56, ICH and GCP guidelines, and applicable pertinent state and federal requirements. For locations participating outside of the US, the IRB or IEC must comply with the applicable requirements of each participating location, including ICH and GCP guidelines, except where a waiver is applicable.

IRBs and IECs must be constituted according to the applicable laws. It is the responsibility of each clinical site to submit the protocol, IB, patient informed consent, patient recruitment materials (if applicable), and other documentation as required by the IRB or IEC for review and approval. A copy of the written approval must be provided to the Sponsor.

The documentation should clearly mention the approval/favorable opinion of the protocol, the patient informed consent form, and patient recruitment materials (if applicable), including respective version dates. The written approval and a list of the voting members, their titles or occupations, and their institutional affiliations must be obtained from the IRBs or IECs and provided to the Sponsor prior to the release of clinical study supplies to the clinical site and commencement of the study. If any member of the IRB or IEC has direct participation in this study, written notification regarding his or her abstinence from voting must also be obtained.

Clinical sites must adhere to all requirements stipulated by their respective IRB or IEC. This includes notification to the IRB or IEC regarding: protocol amendments, updates to the ICD, recruitment materials intended for viewing by patients, aggregate safety reports required by regulatory competent authorities, serious and unexpected AEs, reports and updates regarding the ongoing review of the study at intervals specified by the respective IRB or IEC, and submission of final study reports and summaries to the IRB or IEC.

It is the responsibility of each clinical site to submit information to the appropriate IRB or EC for annual review and annual re-approval.

The Investigator must promptly inform their IRB or IEC of all SAEs or other safety information reported from the patient or the Sponsor.

15.2. Ethical Conduct of the Study

The investigator agrees, when signing the protocol, to conduct the study in accordance with ethical principles that have their origin in the current revision of the Declaration of Helsinki and are consistent with ICH/GCP, applicable regulatory requirements, and policies and procedures as outlined by the ethical requirements for IRB or IEC review and ICDs.

The Investigator agrees to allow monitoring and auditing of all essential clinical study documents by the Sponsor or its authorized representatives and inspection by the FDA, EMA, or other appropriate regulatory authorities. Monitoring and auditing visits by the Sponsor or

Bempedoic Acid Clinical Study Protocol 1002-050

authorized designee will be scheduled with the appropriate staff at mutually agreeable times periodically throughout the study.

The Investigator will assure proper implementation and conduct of the study, including those study-related duties delegated to other appropriately qualified individuals. The Investigator will assure that study staff cooperates with monitoring and audits, and will demonstrate due diligence in recruiting and screening study patients. The Investigator must sign and return to the Sponsor the "Investigator's Signature" page (see Appendix 3) and provide a copy of current curriculum vitae. For this study and all studies conducted under an IND, the Investigator must sign and return a completed Form FDA 1572 "Statement of Investigator" to the Sponsor (or designee). For European Union (EU) investigators, equivalent information contained within the FDA 1572 form may be requested unless a waiver has been requested and received by the Sponsor from the FDA.

15.3. Written Informed Consent

The Principal Investigator(s) at each center will ensure that the patient is given full and adequate oral and written information about the nature, purpose, possible risk and benefit of the study. Patients must also be notified that they are free to discontinue from the study at any time. The patient should be given the opportunity to ask questions and allowed time to consider the information provided.

The patient's signed and dated informed consent must be obtained before conducting any study procedures.

A separate informed consent will be obtained for collecting the genetic blood sample.

The Principal Investigator(s) must maintain the original, signed ICD. A copy of the signed ICD must be given to the patient.

15.4. Patient Confidentiality

The names and identities of all research patients will be kept in strict confidence and will not appear on eCRFs or other records provided to or retained by the Sponsor (or the Sponsor's authorized representative). If a patient's name appears on any document, it must be redacted and replaced with the patient identifier before a copy of the document is supplied to the Sponsor or Sponsor's authorized representative. The ICD must include appropriate statements explaining that patient data will be confidential and what actions will be taken to ensure patient confidentiality.

Any other confidentiality requirements specified by the site, IRB or IEC, or national or local regulations will be adhered to and detailed appropriately in the ICD.

16. DATA HANDLING AND RECORDKEEPING

16.1. Inspection of Records

Applicable regulations require the Sponsor (or the Sponsor's authorized representative) to inspect all documents and records to be maintained by the Investigator, including but not limited to, medical records (office, clinic, or hospital) for the patients in this study. These regulations also allow the Sponsor's records to be inspected by authorized representatives of the regulatory agencies. The Investigator will permit study-related monitoring, audits, IRB or IEC review, and regulatory inspections by providing direct access to source data/documents. Direct access includes permission to examine, analyze, verify, and reproduce any records and reports that are important to the evaluation of a clinical study.

16.2. Retention of Records

In compliance with the ICH/GCP guidelines, the Investigator/Institution agrees to retain and maintain all study records that support the data collected from each patient, as well as all study documents as specified in ICH/GCP, Section 8 Essential Documents for the Conduct of a Clinical Trial. The Investigator agrees to contact the Sponsor before destroying or relocating any study documentation and is expected to take measures to prevent accidental or premature destruction of these documents.

If the Investigator retires, relocates, or for other reasons withdraws from the responsibility of keeping the study records, custody must be transferred to a person who will accept responsibility. The Sponsor must be contacted in writing regarding the name and address of the new person responsible as well as the disposition of document storage. Under no circumstances shall the Investigator relocate or dispose of any study documents before having obtained written approval from the Sponsor.

Essential records (including eCRFs, source documents, study drug disposition records, signed patient ICDs, AE reports, and other regulatory documents) as required by the applicable regulations, must be maintained for 2 years after a marketing application is approved for the drug for the indication for which it is being investigated; or, if no application is to be filed or if the application is not approved for such indication, until 2 years after formal discontinuation of clinical development of the investigational product.

It is the responsibility of the Sponsor to inform the Investigator/Institution as to when these documents no longer need to be retained.

16.3. Case Report Forms and Study Records

Access to eCRFs will be provided to the clinical site. As part of the responsibilities assumed by participating in the study, the Investigator agrees to maintain adequate case histories for the patients treated as part of the research under this protocol. The Investigator agrees to maintain accurate source documentation and eCRFs as part of the case histories.

Study records are comprised of source documents, eCRFs, and all other administrative documents (eg, IRB or IEC correspondence, clinical study materials and supplies shipment

manifests, monitoring logs, and correspondence). A study-specific binder will be provided with instructions for the maintenance of study records.

Source documentation is defined as any handwritten or computer-generated document that contains medical information or test results that have been collected for or in support of the protocol specifications (eg, laboratory reports, clinic notes, study drug disposition log, pharmacy records, patient sign-in sheets, patient completed questionnaires, telephone logs, X-rays, and ECGs). All draft, preliminary, and pre/final iterations of a final report are also considered to be source documents (eg, faxed and hard copy of laboratory reports, faxed and hard copy of initial results, and final report).

The Investigator agrees to allow direct access to all essential clinical study documents for the purpose of monitoring and/or auditing by the Sponsor or its authorized representatives and inspection by the appropriate regulatory authorities.

Data reflecting the patient's participation with the study drug under investigation are to be reported to the Sponsor. The data are to be recorded on the eCRFs and/or other media provided or approved by the Sponsor.

A completed eCRF must be submitted for each patient who receives study drug, regardless of duration. All supportive documentation submitted with the eCRF, such as laboratory or hospital records, should be clearly identified with the study and patient number. Any personal information, including patient name, should be removed or rendered illegible to preserve individual confidentiality. The eCRF should not be used as a source document unless otherwise specified by the Sponsor.

Neither the Sponsor nor a service provider contracted to analyze data and complete the study report is permitted to interpret a blank answer; therefore, all fields should be completed. All requested information must be entered on the eCRFs. If an item is not available or is not applicable, this fact should be indicated as not available (N/A) or not done (N/D); do not leave a field blank.

Each set of completed eCRFs must be signed and dated by the Investigator acknowledging review and that the data are accurate and complete. The completed database is to be returned to the Sponsor as soon as practical after completion by the mechanism prescribed for the protocol.

It is essential that all dates appearing on the Sponsor's patient data collection forms for laboratory tests, cultures, etc, be the dates on which the specimens were obtained or the procedures performed. The eCRFs will be electronically signed by the Investigator and dated as verification of the accuracy of the recorded data. All data collection forms should be completed within 48 hours following the evaluation.

17. ADMINISTRATIVE CONSIDERATIONS

17.1. Investigators

The Investigator must agree to the responsibilities and obligations listed below, as specified by the appropriate FDA/EMA regulatory requirements or ICH/GCP guidelines:

- Agree to conduct the study in accordance with the relevant current protocol
- Agree to personally conduct or supervise the described investigation(s)
- Agree to inform any patients, or persons used as controls, that the study drugs are being used for investigational purposes and ensure that the requirements relating to obtaining informed consent and IRB/IEC review and approval are met
- Agree to report adverse experiences that occur during the course of the investigation(s)
- Read and understand the information in the IB, including the potential risks and side effects of the study drug
- Ensure that all associates, colleagues, and employees assisting in the conduct of the study are informed about their obligations in meeting the above commitments
- Maintain adequate and accurate records and make those records available for inspection
- Ensure that an appropriate IRB/IEC will be responsible for the initial and continuing review and approval of the clinical investigation
- Agree to promptly report to the IRB/IEC all changes in the research activity and all unanticipated problems involving risks to patients or others
- Agree to not make changes in the research without IRB/IEC approval, except where necessary to eliminate apparent hazards to patients
- Comply with all other requirements regarding the obligations of clinical Investigators and all other pertinent requirements.

Refer also to:

- FDA Regulations Related to GCP and Clinical Trials: http://www.fda.gov/oc/gcp/regulations.html
- Guidance and Information Sheets on GCP in FDA-Regulated Clinical Trials: http://www.fda.gov/oc/gcp/guidance.html
- Guidance for IRBs and Clinical Investigators: http://www.fda.gov/oc/ohrt/irbs/default.htm
- DIRECTIVE 2001/20/EC: http://ec.europa.eu/health/files/eudralex/vol-1/dir 2001 20/dir 2001 20 en.pdf
- Guidance for Industry E6 Good Clinical Practice: Consolidated Guidance: http://www.fda.gov/cder/guidance/959fnl.pdf

17.2. Amendments

Changes to the research covered by this protocol must be implemented by formal protocol amendment. All amendments to the protocol must be initiated by the Sponsor and signed and dated by the Investigator. Protocol amendments must not be implemented without prior IRB or IEC approval. Documentation of amendment approval by the Investigator and IRB or IEC must be provided to the Sponsor or its authorized representative. When the change(s) involve only logistic or administrative aspects of the study, the IRB or IEC only needs to be notified.

During the course of the study, in situations where a departure from the protocol is unavoidable, the Investigator will contact the Medical Monitor. Except in emergency situations, this contact should be made before implementing any departure from the protocol. In all cases, contact with the Medical Monitor must be made as soon as possible to discuss the situation and agree on an appropriate course of action. The data recorded on the eCRF and source documents will reflect any departure from the protocol and the source documents will describe the departure and the circumstances requiring it.

17.3. Financial Disclosure

Prior to the start of the study, Investigators will release sufficient and accurate financial information that permits the Sponsor to demonstrate that an Investigator and all study relevant assigned personnel have no personal or professional financial incentive regarding the future approval or disapproval of the study drug such that his or her research might be biased by such incentive.

18. PUBLICATION AND DISCLOSURE POLICY

It is understood by the Investigator that the information and data included in this protocol may be disclosed to and used by the Investigator's staff and associates as may be necessary to conduct this clinical study.

All information derived from this clinical study will be used by the Sponsor (or designee) and therefore, may be disclosed by the Sponsor (or designee) as required to other clinical Investigators, to the FDA, EMA, and to other government agencies, or in connection with intellectual property filings or publications. In order to allow for the use of the information derived from this clinical study, it is understood by the Investigator that there is an obligation to provide the Sponsor with complete test results and all data from this clinical study. The Investigator agrees to maintain this information in confidence, to use the information only to conduct the study, and to use the information for no other purpose without the Sponsor's prior written consent (or as otherwise may be permitted pursuant to a written agreement with the Sponsor or its designee).

The results of the study will be reported in a clinical study report prepared by the Sponsor (or designee), which will contain eCRF data from all clinical sites that conducted the study.

The Sponsor shall have the right to publish data from the study without approval from the Investigator. Manuscript(s) and abstract(s) may only be prepared through cooperation between the Sponsor (or designee) and the study Investigator(s). If an Investigator wishes to publish information from the study, a copy of the manuscript must be provided to the Sponsor for review in accordance with the provisions of such Investigator's written agreement with the Sponsor (or designee) before submission for publication or presentation. If requested by the Sponsor in writing, the Investigator will withhold such publication in accordance with the provisions of such agreement.

20. APPENDICES

| Appendix 1: | Schedule of Events (Patient Visit Schedule) |
|-------------|---|
| Appendix 2: | Sponsor's Signature |
| Appendix 3: | Investigator's Signature |
| Appendix 4: | Summary of Changes in Amendment 1 |

Appendix 5: Summary of Changes in Amendment 2

APPENDIX 1. SCHEDULE OF EVENTS (PATIENT VISIT SCHEDULE)

| Month | 0 | 3 | 6 | 9 | 12 | 15 | 18/EOT ¹ | 19/EOS ² |
|-----------------------------------|-------------------|---------|---------|---------|---------|---------|---------------------|---------------------|
| Week | EOS Parent | Wk 12 | Wk 24 | Wk 36 | Wk 52 | Wk 64 | Wk 78 | Wk 82 |
| Visit Window | 30 Days pre-M0 | ±7 days | +14 days |
| In-clinic Visit | X | X | | | X | | X | X |
| Phone Visit | | | X | X | | X | | |
| Procedure | | | | | | | | |
| Informed Consent | X | | | | | | | |
| Enrollment Criteria | X | | | | | | | |
| Medical History | X | | | | | | | |
| Concomitant Medications | X | Х | X | X | X | X | Х | X |
| Adverse Event Recording | X | Х | Х | Х | Х | X | Х | X |
| Physical Exam | X | | | | Х | | X | |
| Weight ³ | X | Х | | | X | | Х | Х |
| Vital Signs ⁴ | X | Х | | | Х | | Х | Х |
| Urine Pregnancy Test ⁵ | X | | | | | | | |
| Clinical Safety Labs ⁶ | X | Х | | | X | | Х | X |
| Basic Fasting Lipids ⁷ | X | Х | | | X | | X | X |
| Coagulation ⁸ | X | | | | | | | |
| ApoB and hsCRP | X | Х | | | Х | | Х | Х |
| HbA _{1C} | X | | | | X | | Х | X |
| IWRS Contact9 | X | Х | | | Х | | Х | |
| Drug Dispensing | X | Х | | | Х | | | |
| Drug Return/ Compliance | | Х | | | Х | | Х | |

NOTE: For patients who withdraw from study drug treatment, but consent to be followed for safety assessments and return to clinic for these visit, the visits will occur according to the protocol schedule. Safety assessments should include clinical safety and basic lipid laboratories, adverse events (AEs), physical examination (PE), and vital signs. For patients who withdraw from study drug treatment, but consent to be followed for safety assessments by phone, the telephone contacts will occur according the protocol schedule with information regarding current health status and to collect information on AEs (eg, recent procedures, hospitalizations, and if the patient has died, the cause of death). If a patient does not provide consent to be followed for safety assessments per the protocol (either by returning to clinic or by phone), Visit Week 78/End of Treatment (EOT) will be scheduled as soon as possible and the patient will be asked to come back 4 weeks after last investigational medicinal product (IMP) dose for Visit Week 82/End of Study (EOS). No further visits will be scheduled.

Bempedoic Acid Clinical Study Protocol 1002-050

- ¹ All procedures will be completed for all patients at either EOT or early withdrawal.
- ² All procedures will be completed for all patients 4 weeks after last IMP dose if completing the study or early withdrawal.
- ³ Body weight will be measured in the morning while fasting, using consistent scales, after voiding, and without shoes and outerwear (eg, coats).
- ⁴ Vital signs will include diastolic blood pressure (DBP), systolic blood pressure (SBP), heart rate (HR) and will be collected prior to any blood sample collection. Patient will rest for 5 minutes prior to assessments
- ⁵ Urine pregnancy test in women of childbearing potential only
- ⁶ Clinical safety labs include hematology, blood chemistry, and urinalysis at all visits. Please refer to laboratory manual for detailed schedule of tests.
- ⁷ Basic fasting lipids include total cholesterol (TC), calculated low-density lipoprotein cholesterol (LDL-C), highdensity lipoprotein cholesterol (HDL-C), non-HDL-C,), and triglycerides (TG).
- ⁸ Only in patients receiving anticoagulant therapy that in the investigator's judgment require monitoring at Month 0 and 3 to 5 days post-Month 0
- ⁹ Interactive web response system (IWRS) contact at either an early withdrawal or an EOS visit to register study discontinuation visit date

Bempedoic Acid Clinical Study Protocol 1002-050

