9.2.6. Treatment Month 18/EOT (Week 78 ±7days)

Patients will undergo the following assessments and procedures when completing the End of Treatment (EOT) visit, withdrawing from study prior to Week 78 (early withdrawal), or withdrawing from IMP treatment:

- Concomitant medication review (ongoing)
- Assess AEs, SAEs, and potential clinical endpoints
- Weight
- Vital signs
- Physical exam
- Clinical laboratory evaluations:
 - Hematology, blood chemistry, and urinalysis
 - Basic fasting lipids (TC, calculated LDL C, HDL C, non-HDL C, and TG)
 - ApoB and hs-CRP
 - HbA_{1C}
- Return of IMP; assessment and recording of IMP compliance
- Complete study status in IWRS (ie, early withdrawal or completed study).

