9.2.7. Off Study Drug Period Month 19/EOS (Week 82 +14 days)

Patients will return for a final EOS visit 4 weeks after IMP treatment has been completed (including patients who withdraw from IMP treatment prior to Week 78) to undergo the following assessments and procedures.

- Concomitant medication review
- Assess AEs, SAEs, and potential clinical endpoints
- Weight
- Vital signs
- Clinical laboratory evaluations:
 - hematology, blood chemistry, and urinalysis
 - Basic fasting lipids (TC, calculated LDL C, HDL C, non-HDL C, and TG)
 - ApoB and hs-CRP
 - HbA_{1C}

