12. STATISTICS

12.1. General Considerations

Statistical analyses in this open label, multicenter single arm study will be descriptive in nature. No statistical inference is planned. Patient disposition, demographics and baseline characteristics will be summarized. Summary statistics for continuous variables will include the number of patients, mean, median, standard deviation or standard error, first and third quartiles minimum, and maximum. For categorical variables, the frequency and percentage will be given. Ninety-five percent (95%) confidence intervals (CIs) will be calculated for select continuous and categorical endpoint estimates. All patients will be summarized together as well as by their prior treatment group in the parent study.

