- Revised the study design to include an assessment at Week 82, 4 weeks after patients have completed their last dose of bempedoic acid. This assessment was added to have safety and efficacy data off study drug to help interpret any potential findings during the treatment period.
- Updated the design schematic to include the 4-week follow-up period from Week 78 to Week 82.
- Week 78 is now called the End of Treatment (EOT) visit and Week 82 is described as the Off Study Drug Period/End of Study (EOS) visit.
- The section on Background of Bempedoic Acid has been updated to reflect the current version of the Investigator's Brochure.

- The section on Concomitant Medications has been revised to avoid changes in lipidlowering medications during the 4-week washout period to limit the introduction of medications that may affect endpoints of interest measured at Week 82.
- The statistical analysis plan for renal events was updated to remove text that indicated muscle related events would be analyzed based on baseline eGFR. There is no data or clinical justification to justify assessment of muscle related events by eGFR.
- Text throughout the protocol was updated to reflect the addition of the 4-week follow-up period.
- Typographical errors and formatting were corrected or revised based on these changes or to improve clarity and consistency.

| Location: | |
|------------------------|-----|
| Title Page | |
| Original Text: | |
| Sponsor Contact | |
| Medical Monitor | •• |
| New Text: | |
| Sponsor Contact | • • |
| Medical Monitor | •• |

CHANGE 1 REVISION OF TITLE PAGE VERSION INFORMATION

Original Text:

| | Version | Date | |
|-----------|--------------------|------------------|--|
| | Original Protocol: | 01 November 2017 | |
| | Amendment 1: | 9 May 2017 | |
| New Text: | | | |
| | Version | Date | |
| | Original Protocol: | 01 November 2017 | |
| | | | |
| | Amendment 1: | 09 May 2017 | |

CHANGE 2 REVISION TO THE STUDY DESIGN TO INCLUDE A 4 WEEK FOLLOW UP PERIOD AFTER WEEK 78

Location:

Section 2, Synopsis; Section 6.1, Overall Study Design; Section 6.3, Study Duration; Section 6.4, End of Study; Section 9.2.6, Treatment Month 18; Section 9.2.7, Washout Month 19; Section 9.3.1, Early Withdrawal from the Study; Section 9.3.2, Procedures for Early Withdrawal

Original Text:

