#### 5.2.2 **Protocol Violations and Deviations**

A full list of protocol violations and deviations will be compiled and reviewed by the clinical team to identify key versus non-key violations/deviations before final database lock. For violations at study entry, patients will be assessed against the inclusion and exclusion criteria of the protocol. For on-study deviations, compliance with the protocol will be examined with regard to prohibited therapies, and timing and availability of planned assessments. The final list of protocol deviation will be approved by the study team prior to interim analysis cut of or final database lock, and will be used to generate the protocol deviation summary and listing.

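### SAP v1.3 gives the Week 82 visit window as 574±14 days where the protocol allows +14 only, and its analysis window can admit samples 10 days off drug to the off-drug summary

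*Protocol*

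**What the plan says.** **Protocol.** Section 9.2.7 is headed "Off Study Drug Period Month 19/EOS (Week 82 +14 days", and the window row of Appendix 1 reads "30 Days pre-M0 | ±7 days | +14 days" for Month 0, Weeks 12 to 78 and Week 82 in turn. Neither gives an early allowance for Week 82. Appendix 1, footnote 2, ties the visit to dosing: "All procedures will be completed for all patients 4 weeks after last IMP dose if completing the study or early withdrawal". Sections 9.2.7 and 9.3.2 give the same 4-week rule. The preceding visit has a two-sided window: "Treatment Month 18/EOT (Week 78 ±7days". The summary of changes for Amendment 2 gives the reason for Week 82: "This assessment was added to have safety and efficacy data off study drug to help interpret any potential findings during the treatment period".

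**SAP v1.3.** The visit table in section 5.1 gives Week 82 a target of Day 574. Its bottom row, labelled as the protocol-defined windows, gives 574±14. The same figure stands in v1.1 and v1.2. Appendix 1 of SAP v1.3 gives +14 days, in line with the protocol. A separate row assigns data to visits: Days 498 to 562 are Week 78 and Day 563 onward is Week 82. Section 4.6 declares no change from the planned analyses.

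On deviations, section 5.2.2 says "compliance with the protocol will be examined with regard to prohibited therapies, and timing and availability of planned assessments". Section 5.3 includes Week 82 among the visits summarised for each lipid parameter, with 95% confidence intervals at post-baseline visits.

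**The concern.** Week 82 was added to show what happens off drug, so its value depends on how long each patient had been off drug when sampled. The SAP handles that interval loosely in two places.

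First, the row that claims to report the protocol's window does not match it. It allows visits 14 days early, and it counts from first dose where the protocol counts 4 weeks from last dose. A deviation listing built from that row would pass early visits as on time.

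Second, the row that selects the data is also counted from first dose and opens at Day 563, 11 days before the target. Samples taken well short of 4 weeks off drug can therefore be averaged into the off-drug result, and nothing in the SAP would show the reader that this had happened. Early visits are foreseeable: protocol section 9.3.2 says the sponsor will consider accommodating them.

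**Working it through.** **Inputs.** Week 78 target Day 546, window ±7 (protocol 9.2.6). Week 82 target Day 574, protocol-defined row 574±14, analysis windows [498,562] and [563,∞] (SAP v1.3 section 5.1). Protocol window +14 days, visit 4 weeks after last dose (protocol 9.2.7 and Appendix 1). Assumption: the last dose falls on the day of the end-of-treatment (EOT) visit.

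**Step 1: reproduce the plan's figures.** Target day = 7 × week: 7 × 78 = 546 and 7 × 82 = 574, both as stated. The ±14 does not reproduce. On a Day 574 anchor the protocol's window is 574 to 574 + 14 = 588. The SAP row gives 574 − 14 = 560 to 588.

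**Step 2: range of EOT days.** 546 − 7 = 539 to 546 + 7 = 553.

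**Step 3: shortest time off drug under each rule.** Days off drug = visit day − last-dose day.

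| Earliest Week 82 day | EOT Day 539 | EOT Day 546 | EOT Day 553 |
|---|---|---|---|
| Day 560 (lower edge of 574±14) | 21 | 14 | 7 |
| Day 563 (first day analysed as Week 82) | 24 | 17 | 10 |
| Day 574 (+14 only, fixed-day anchor) | 35 | 28 | 21 |
| Last dose + 28 (protocol's dose anchor) | 28 (Day 567) | 28 (Day 574) | 28 (Day 581) |

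On the dose anchor with +14 days, the interval is 28 to 42 days off drug whatever the EOT day. The fixed-day and dose anchors agree only when the last dose is on Day 546.

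**Step 4: compare the two SAP rows.** Days 560, 561 and 562 lie inside 574±14 but also inside [498,562]. They pass as on time for Week 82 and are analysed as Week 78. SAP v1.3 gives no rule for choosing between two values in one window, so an off-drug value could sit beside, or displace, the true EOT value. The earliest visit that is both inside 574±14 and analysed as Week 82 is Day 563.

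**Step 5: patients who stop early.** Protocol 9.3.2 asks them to return 4 weeks after the last dose, and 9.3.1 asks them to keep to the visit schedule. If a patient stops on Day 364, the Week 52 target, the 4-week visit falls on 364 + 28 = Day 392. Assigned by study day alone, it falls in the Week 52 window [309,406], although it is an off-drug sample.

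**The case against.** The strongest reply is that the ±14 cell is a transcription slip with no effect on the results. The row it sits in selects no data and defines no analysis set. Changing ±14 to +14 alters no Week 82 mean, because [563,∞] decides what is summarised. This stands, and it is why correcting the cell alone is not enough.

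A second reply is that section 5.2.2 examines compliance with the protocol, which says +14, and that the SAP overrides the protocol only on plans for data analysis. Nothing states that deviations will be programmed from the 574±14 cell. This also stands, so the unflagged-visit point is conditional.

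Third, sites are told to schedule the visit 4 weeks after the last dose. The shortest intervals need a late EOT visit followed by an early final visit, and the documents give no frequency for that. Week 82 is not a declared endpoint, and of the analysis as a whole the protocol says "No statistical inference is planned". These points limit the importance of the problem without removing it.

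A reader might infer something stronger: that samples only 7 days off drug are reported as the Week 82 result. The documents do not support that. A 7-day interval needs a visit on Day 560, which [498,562] assigns to Week 78. A reader might also set the full span of 574±14 (7 to 49 days off drug) against the protocol's 28 to 42. That mixes two anchors: the 49 (588 − 539) arises under +14 on a fixed Day 574 as well.

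**Conclusion.** The SAP misstates the protocol's Week 82 window and contradicts its own Appendix 1. That part is certain. Two consequences follow, and they should be kept apart.

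- **Deviation check.** If section 5.2.2 uses the 574±14 row, visits up to 14 days before Day 574 go unflagged, at worst 7 days off drug.
- **Off-drug summary.** Whatever that row says, [563,∞] admits samples as little as 10 days after an in-window EOT visit, or 17 days if EOT was on target, against the protocol's 4 weeks. Days 560 to 562 go the other way and are analysed as Week 78.

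These counts assume that the last dose is on the EOT day and that EOT is within its ±7 window; an earlier last dose or an out-of-window EOT visit changes them. The number of patients affected is unknown. How far any Week 82 mean would move cannot be estimated, because the documents as available give no rate at which the effect is lost.

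The primary endpoint, incidence of treatment-emergent adverse events, is unaffected. The Week 52 and 78 endpoints are largely unaffected, apart from off-drug samples that fall into those windows. This is a minor to moderate issue, worth correcting because the Week 82 summary exists to describe patients off drug.

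**What to change.** In SAP v1.3:

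1. Reconcile the 574±14 cell in section 5.1 with the protocol's window (+14 days, 4 weeks after last dose), and state that the timing check in 5.2.2 uses the reconciled window.
2. Classify Week 82 values by days since last dose as well as by study day, so that post-treatment samples are not summarised as Week 78 or another on-treatment visit.
3. Report days from last dose to the Week 82 sample, by prior treatment group and overall. Flag values drawn earlier than the protocol's 4 weeks, or show the Week 82 summary with and without them.
4. For patients who stop drug early, keep the visit 4 weeks after last dose distinct from any later scheduled Week 82 visit.

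This restates the protocol's own timing and proposes no new visit rule. The date of last dose is already recorded (protocol 9.3.2 requires it at withdrawal, and the SAP uses it for exposure), so no new data are needed. The cost is a few more visits listed as out of window and slightly more programming, chiefly for items 2 and 4.
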